#### 9.2 Adverse Event Definition:

An adverse event (AEs) includes any complication whose clinical significance is greater than anticipated, or which occurs with a frequency greater than that which is usually seen for this type of device. A serious adverse event (SAE) is defined as an event that,

- results in death
- is life-threatening (places the subject at immediate risk of death from the experience as it occurred)
- results in a persistent or significant disability/incapacity (substantial disruption of one's ability to carry out normal life functions)
- results in medical or surgical intervention
- results in or prolongs an existing hospitalization (even if the hospitalization is a precautionary measure for observation)

An unanticipated adverse device effect (UADE) is any serious adverse effect related to the device that meets the definition above or any other unanticipated serious problem associated with a device that relates to the rights, safety, or welfare of subjects. Investigators must report all SAE and/or UADE to Tactile Medical within 72 hours of first learning of the event. SAE and/or UADE will be reported in writing to the appropriate IRB in accordance with their policy.

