#### 9.3 Adverse Event Reporting:

Investigators will be responsible for reporting the following pre-defined adverse events regardless of severity, to Tactile Medical in a timely manner:

- New or worsening ulceration

- Clinically worsened or new onset heart failure
- Increase in leg swelling greater than 20%
- Skin irritation/blistering
- Infection of the study limb(s)
- Other – an AE that according to the investigator’s opinion is significant and requires reporting to Tactile Medical but doesn’t necessarily meet the definition of the pre-defined AEs or an SAE

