#### 12.6.5 Safety Endpoint Analysis

The following analyses will be carried out on the Safety Populations. ACTitouch® treated subjects will be compared with multi-layer bandaging treated subjects in terms of:

- the difference in the incidence of ulcer-related adverse events (defined as ulcer infections, maceration, allergic reaction to dressing, or hospitalization for worsening VLU) at 16 weeks using the Kruskal-Wallis test.
- the difference in the incidence of ulcer infections at 16 weeks using the Kruskal-Wallis test.
- the difference in the incidence of ulcer maceration at 16 weeks using the Kruskal-Wallis test.
- the difference in the incidence of allergic reactions to dressing at 16 weeks using the Kruskal-Wallis test.
- the difference in the incidence of hospitalization for worsening VLU at 16 weeks using the Kruskal-Wallis test.

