8.2.3 Other Safety Analyses

The following analyses will be carried out on the Safety Populations. ACTitouch® treated subjects will be compared with multi-layer bandaging treated subjects in terms of:

- the difference in the incidence of ulcer-related adverse events (defined as ulcer infections, maceration, allergic reaction to dressing, or hospitalization for worsening VLU) at 16 weeks using the Cochrane-Mantel-Haenszel (CMH) test (Table 14.3.3).

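### Maceration and allergic reaction to dressing are components of the ulcer-related safety endpoint but have no named reporting category, so their counts may be incomplete

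*Protocol*

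**What the plan says.** Protocol 12.6.5 and SAP 8.2.3 give the ulcer-related composite in the same words: "defined as ulcer infections, maceration, allergic reaction to dressing, or hospitalization for worsening VLU". Protocol 12.2 makes this comparison the safety objective. Protocol 12.6.5 also tests maceration and allergic reaction separately, and SAP Table 14.3.3 gives each its own row and p-value.

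Collection is governed by two sections:

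- Protocol 9.2 describes an adverse event as taking in "any complication whose clinical significance is greater than anticipated, or which occurs with a frequency greater than that which is usually seen", with similar devices as the yardstick. Its criteria for a serious event include one that "results in or prolongs an existing hospitalization".
- Protocol 9.3 begins "Investigators will be responsible for reporting the following pre-defined adverse events regardless of severity" and names five categories: new or worsening ulceration, new or worse heart failure, leg swelling up by more than 20%, "Skin irritation/blistering", and infection of the study limb. A sixth line, Other, covers "an AE that according to the investigator’s opinion is significant and requires reporting to Tactile Medical".

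Neither section mentions maceration or allergic reaction.

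**The concern.** A pre-specified endpoint needs a collection rule that feeds it. For two of the four components the written rule leaves the decision to the site. Whether an event occurs more often than usual cannot be judged from one subject, and mild maceration under compression may well be seen as no worse than anticipated. Protocol 9.1 already lists itching and flaking skin among symptoms that any subject may have, which invites the same view of a mild dressing reaction.

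Two things are at stake. Sites (about 30 are planned) may apply different thresholds, which adds noise and removes events from Table 14.3.3. Capture may also differ between arms in an open-label trial with unequal visit schedules, which could bias the comparison. The background in Protocol 3.1 reports that an earlier trial of the device found advantages in exudate management and skin protection. Maceration is close to that territory, so it is a component on which the arms could plausibly differ.

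**Working it through.** The plan states no incidence, power or sample size for the safety endpoint, so there is no figure to reproduce. The main check sets the endpoint against the reporting rules.

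**Step 1. Trace each component to a reporting route.**

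| Component (12.6.5, SAP 8.2.3) | Route by name | Indirect route |
|---|---|---|
| Ulcer infection | 9.3, infection of the study limb | not needed |
| Hospitalization for worsening ulcer | 9.2, serious-event criterion | not needed |
| Allergic reaction to dressing | none | skin irritation/blistering if recorded as such; Other |
| Maceration | none | Other; perhaps irritation in some cases |

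Two of four have an explicit route and two of four have none by name. Maceration has the weaker cover.

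**Step 2. Check whether visit assessments fill the gap.** Protocol 7.6 has staff assess drainage, wound margin and periwound areas, and 7.10 has the legs examined for irritation, trauma and ulceration. Neither names maceration or allergy, and nothing shown carries these findings into the adverse-event data. SAP 8.2.1 codes events with internal sponsor codes that are not reproduced. An event entered as irritation would need a rule to be counted as an allergic reaction or maceration in Table 14.3.3, and none is given.

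**Step 3. Compare opportunities to observe.** Protocol 6.4 schedules weekly visits for bandaging (16) and visits at weeks 1, 2, 4, 6, 9, 12 and 16 for ACTitouch (7). Subjects who heal have fewer. Protocol 6.5 adds 2 + 9 = 11 ACTitouch support contacts by text or phone, which do not involve inspecting the leg.

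**Step 4. Illustrate the effect of incomplete capture.** Every rate here is an assumption. Let s be the share of composite events that are maceration or allergy only, and c the fraction of those captured, equal in both arms. Observed incidence is the true incidence times f = 1 − s(1 − c). Power is for an unstratified two-proportion test, two-sided 0.05, with the Protocol's planned 102 per arm.

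| True rates | s | c | f | Observed rates | Power |
|---|---|---|---|---|---|
| 15% vs 30% | any | 1 | 1 | 15% vs 30% | 73% |
| 15% vs 30% | 0.25 | 0.5 | 0.875 | 13.1% vs 26.3% | 66% |
| 15% vs 30% | 0.5 | 0.5 | 0.75 | 11.3% vs 22.5% | 57% |
| 15% vs 30% | 0.5 | 0 | 0.5 | 7.5% vs 15% | 40% |
| 10% vs 20% | any | 1 | 1 | 10% vs 20% | 52% |
| 10% vs 20% | 0.25 | 0.5 | 0.875 | 8.8% vs 17.5% | 46% |
| 10% vs 20% | 0.5 | 0.5 | 0.75 | 7.5% vs 15% | 40% |
| 10% vs 20% | 0.5 | 0 | 0.5 | 5% vs 10% | 27% |

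The direction is clear; the size depends wholly on the assumed rates, s and c. Unequal capture by arm would add bias, which this table does not show.

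**The case against.** A reader might infer that maceration and dressing reactions will be under-collected, or that mild ones are simply not reportable. The documents do not support that.

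- Protocol 9.2 says what an adverse event includes; it does not say that only such events count. Its threshold does not govern the categories that 9.3 names, and these already cover several expected complications of compression.
- A dressing reaction that shows as irritation or blistering must be reported at any severity, and any event that results in medical or surgical intervention meets a serious-event criterion.
- Periwound areas and skin are assessed at each visit. The CRF, the internal codes and the content of the schedule of activities are not shown, so dedicated fields may exist.
- Unequal visits are a separate matter that naming the events would not remove, and support contacts and unscheduled visits give ACTitouch subjects further chances to report.
- Protocol 12.3.4 lists only the composite, infection and hospitalization as safety endpoints, and no power is stated for a safety hypothesis.

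All of this stands. It lowers certainty about the consequence and rules out extending the point to the overall adverse-event rate in Table 14.3.1 as though shown. It does not supply the missing link: indirect routes still depend on judgement, and no stated source or classification rule feeds two rows of Table 14.3.3.

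**Conclusion.** The point holds as a mismatch between endpoint and collection rule. Two of the four components, each tested separately, have no named category in 9.3 and no stated data source or classification rule. Their ascertainment may therefore rest on investigator discretion, be incomplete, and vary by site.

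A difference by arm is possible because scheduled inspections number 16 against 7. If short-lived maceration is missed between visits, more would be missed with ACTitouch, which would favour the device. The documents do not establish that this will happen.

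The loss cannot be sized from the documents; the power figures are illustrations under assumed rates with equal capture. Confidence is medium, since a CRF with dedicated fields would reduce the point to a missing cross-reference. The sponsor should make the change, which is cheap.

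**What to change.** 1. Add two terms, with definitions, to the Protocol 9.3 list: ulcer or periwound maceration, and allergic reaction to dressing or compression material. Make both reportable at any severity and record them at each visit in both arms. If CRF fields already do this, name them as the source for Table 14.3.3.
2. State that the expectedness threshold in 9.2 does not apply to the components of the ulcer-related endpoint.
3. Add a supportive version of Table 14.3.3 limited to the visits common to both arms (weeks 1, 2, 4, 6, 9, 12 and 16).

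A full rewrite of 9.2 is not needed to cure this mismatch. A definition that started at randomization would also leave out events in the two-week run-in, when consented subjects already wear study bandaging.

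The cost is protocol and possibly CRF wording, modestly more reporting by sites, and one extra table.

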- Subject's target ulcer measures less than 1.5cm^2 at the Randomization Visit.
- Subject appears to have evidence of infection in any ulcer.
- The sum of the ulcer areas on the subject's study limb is > 50cm^2.

5.2.4 Subject Withdrawal or Early Termination:

Subjects will exit the study if they meet any of the following criteria:

- Subject death
- Subject voluntarily withdraws or investigator's decision
- Subject experiences an adverse event that in the investigator's clinical judgment necessitates study discontinuation
- Ulcer recurrence during the 3 month follow up period
- Subject acquires any of the exclusion criteria, except
  - If subject acquires an infection, they may be treated for the infection and continue in the trial in the investigator's discretion. The investigator can instruct the subject to cease sustained or IPC treatment for up to two (2) consecutive weeks but no more than four (4) weeks total. If the subject is required to abstain from study treatment for greater than the amount described above, the subject will be removed from the study.

5.3 Dosage:

Run-in

All subjects will participate in a two week run-in phase. The treatment will include multi-layer compression bandaging which must be worn 24 hours a day except during clinic visits. The run-in phase is intended to assess the subject's initial response to standard of care treatment using multi-layer bandaging before receiving treatment with the investigational device.

VLU Treatment Period

All subjects enrolled will be randomized into either treatment using the ACTitouch system or multi-layer bandaging which consists of either PROFORE or Coban 2.

Investigational Group: Subjects assigned to the ACTitouch system must wear the device in sustained mode during all wakeful hours (at least 12 hours each day) and IPC mode for a minimum of 2 hours each day. Subjects will be instructed to remove the ACTitouch for bathing and when driving or operating machinery, and reapply immediately after these activities.

At each visit the subject’s compliance will be evaluated via the compliance tracker on the ACTitouch device.

Subjects randomized to the ACTitouch arm of the study will also be contacted weekly between study visits by study personnel to support device compliance and answer questions as outlined in Section 7.16.

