#### 7.7 Wound Debridement:

Ulcer debridement will be undertaken as needed per the investigator's clinical decision. The methods of debridement may include enzymatic, sharp, surgical, and mechanical debridement and/or pulse lavage.

7.8 Wound Dressings:  
All subjects will undergo wound dressing changes, either in the clinic or at home. Wound dressing will be selected by the investigator. Generally, “dry ulcers” will require hydrocolloid dressings and “wet ulcers” will require foam or alginate.

7.9 Wound Photograph and Tracing:  
At each study visit, (if applicable) the study ulcer will be photographed and the wound will be traced using the Silhouette™ system (Appendix E).

In addition, at the initial visits all ulcers on the study limb will be photographed and traced to ensure that the sum of the areas is not greater than 50cm^2. Any ulcers that form on the study limb during the course of the study will also be photographed and traced for AE documentation.

The initial visit, enrollment visit, and healed visit image and tracing will be evaluated by a single independent adjudicator to increase integrity and to provide a blinded analysis. Ulcer surface areas that fall on or near the minimum or maximum ulcer surface area allowed for study inclusion will be adjudicated in a timely manner. Study staff will have access to the adjudication results by a time no later than the next scheduled subject visit.

7.10 Tissue/Skin Assessment:  
The subject’s legs will be examined for irritation, trauma and ulceration at each study visit. At any time during the study the investigator may determine that a tissue/skin change requires the subject to be withdrawn from the study.

7.11 Compression Application:  
Application of ACTitouch System:  
The ACTitouch system will be applied by the trained study staff. First the ACTitouch under-sock will be applied. The sock will be in direct contact with the skin and wound dressings and the ACTitouch sleeve will wrap around the pre-covered leg. The ACTitouch will be applied while the subject is seated, with the feet lightly resting on the floor.

Application of Multi-Layer Bandaging:  
The trained study staff will apply the multi-layer bandaging according to manufacturer’s instructions. The multi-layer bandaging will be in direct contact with the skin and the wound dressings.

7.12 Application Timing:  

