Possibly related	xx(xxx.x%)	xx(xxx.x%)	
Not related	xx(xxx.x%)	xx(xxx.x%)	
No Event	xx(xxx.x%)	xx(xxx.x%)	
Outcome			
No Event	xx(xxx.x%)	xx(xxx.x%)	x.xxx
Resolved	xx(xxx.x%)	xx(xxx.x%)	
Resolved w/ sequelae	xx(xxx.x%)	xx(xxx.x%)	
Continuing	xx(xxx.x%)	xx(xxx.x%)	
Lost to follow-up	xx(xxx.x%)	xx(xxx.x%)	
Death	xx(xxx.x%)	xx(xxx.x%)	

TACTILE TABLES - SAP

Condition	Treatment N(%)	Control N(%)	P-value
Patients with SAEs	xx(xxx.x%)	xx(xxx.x%)	x.xxx
Patients Discontinued due to AE	xx(xxx.x%)	xx(xxx.x%)	x.xxx

NOTE: P-value based on Kruskal-Wallis test controlling for stratification. Denominator is the number of patients in the Safety Analysis Set.
^aPatients experiencing more than one adverse event are counted under the maximum severity experienced across events.

TACTILE TABLES - SAP

Sponsor: Tactile Medical Systems
 Protocol: 6010

page 1 of Y

Table 14.3.2 Safety Analysis: Incidence of Adverse Events by Internal AE Code
 Safety sample

Internal AE Code	Treatment N(%)	Control N(%)	p-value ^a
Patients with Adverse Events	xx(xxx.x%)	xx(xxx.x%)	xxxx
AE_CODE XX	xx(xxx.x%)	xx(xxx.x%)	x.xxx
AE_CODE XX	xx(xxx.x%)	xx(xxx.x%)	x.xxx
AE_CODE XX	xx(xxx.x%)	xx(xxx.x%)	x.xxx
AE_CODE XX	xx(xxx.x%)	xx(xxx.x%)	x.xxx
AE_CODE XX	xx(xxx.x%)	xx(xxx.x%)	x.xxx
AE_CODE XX	xx(xxx.x%)	xx(xxx.x%)	x.xxx
AE_CODE XX	xx(xxx.x%)	xx(xxx.x%)	x.xxx
AE_CODE XX	xx(xxx.x%)	xx(xxx.x%)	x.xxx
AE_CODE XX	xx(xxx.x%)	xx(xxx.x%)	x.xxx
AE_CODE XX	xx(xxx.x%)	xx(xxx.x%)	x.xxx

Note: A patient experiencing multiple incidences of an event with the same internal AE code is counted only once.
^a P-value calculated from CMH Test.

TACTILE TABLES - SAP

Sponsor: Tactile Medical Systems
 Protocol: 6010

page 1 of Y

Table 16.2.7.1 Listing of Adverse Events
 Safety sample

Treatment Group	Patient ID	Onset Date (Study Day)	Stop Date (Study Day)	Internal AE Code	Serious	Duration	Severity	Causality	Outcome
xxx	xx	ddmmyy (xx)	ddmmyy(xx)	xx	xx	xx	xx	xx	xx
xxx	xx	ddmmyy (xx)	ddmmyy(xx)	xx	xx	xx	xx	xx	xx
xxx	xx	ddmmyy(xx)	ddmmyy(xx)	xx	xx	xx	xx	xx	xx
xxx	xx	ddmmyy(xx)	ddmmyy(xx)	xx	xx	xx	xx	xx	xx
xxx	xx	ddmmyy(xx)	ddmmyy(xx)	xx	xx	xx	xx	xx	xx
xxx	xx	ddmmyy(xx)	ddmmyy(xx)	xx	xx	xx	xx	xx	xx
xxx	xx	ddmmyy(xx)	ddmmyy(xx)	xx	xx	xx	xx	xx	xx
xxx	xx	ddmmyy(xx)	ddmmyy(xx)	xx	xx	xx	xx	xx	xx
xxx	xx	ddmmyy(xx)	ddmmyy(xx)	xx	xx	xx	xx	xx	xx

TACTILE TABLES - SAP

Sponsor: Tactile Medical Systems
Protocol: 6010

page 1 of Y

Table 14.3.3 Safety Analysis: Incidence of Ulcer-Related Adverse Events at 16 Weeks
Safety sample

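### The SAE definition counts any event that leads to medical or surgical intervention, so a study-limb infection treated as an outpatient is literally an SAE, and the first part of the UADE definition does not require the effect to be unanticipated

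*Protocol*

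**What the plan says.** Protocol section 9.2 opens its list of seriousness criteria with "A serious adverse event (SAE) is defined as an event that" and gives five alternatives: death, threat to life, lasting or significant disability, intervention, and new or prolonged hospitalization. The intervention criterion reads in full "results in medical or surgical intervention".

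The same section says that "An unanticipated adverse device effect (UADE) is any serious adverse effect related to the device that meets the definition above", and then adds other unanticipated serious problems linked to a device. SAEs and UADEs go to the sponsor within 72 hours, and to the IRB in line with its policy.

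Section 9.3 lists pre-defined AEs that are reported promptly whatever their severity. They include new or worsening ulceration, skin irritation or blistering, and infection of the study limb. Section 5.2.4 says: "If subject acquires an infection, they may be treated for the infection and continue in the trial". Section 7.7 says: "Ulcer debridement will be undertaken as needed".

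Section 11.4 gives the DSMB the task of reviewing SAEs. SAP Table 14.3.1 has a row "Patients with SAEs" with a p-value for the comparison between arms. The abbreviated SAP tabulates, tests and lists SAEs but does not define or narrow the term.

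**The concern.** A seriousness definition should separate events that need urgent attention from those that ordinary care can handle. The intervention criterion, taken at its word, does not. Most events that a clinician acts on lead to some medical intervention, so the line between the 72-hour tier in 9.2 and the routine tier in 9.3 largely disappears for treated events.

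Two uses of the data are at stake. The SAE row in Table 14.3.1 would be tested on a count that combines treated outpatient infections with deaths and hospitalizations. The DSMB would review the same mixture. Sites would also have to decide for themselves whether to add an unwritten qualifier. The protocol plans about 30 centers, so the same clinical event could be an SAE at one and only a pre-defined AE at another.

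The UADE clause carries the problem one step further. If a device-related event becomes an SAE only because it was treated, it also meets the first part of the UADE definition, even if it is of a kind the protocol lists in advance.

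**Working it through.** No arithmetic applies: the point turns on wording, and the plan gives no figure to reproduce. The check sets the passages side by side.

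1. **Is the criterion qualified anywhere?** In 9.2, the life-threat, disability and hospitalization criteria each carry a clarifying parenthesis. The intervention criterion has none: no purpose, no severity threshold, no exclusion for routine care. SAP 8.2.1 and 8.2.2 use seriousness as a recorded attribute and do not restate it.

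2. **Does a treated infection meet it?** Study-limb infection is an AE by listing in 9.3, whatever its severity. Section 5.2.4 foresees that it may be treated and the subject kept in the trial. Treatment of an infection is a medical intervention that results from the event. The criterion is met, so the event is an SAE with a 72-hour report.

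3. **Does the general AE sentence exclude it?** Section 9.2 first describes AEs as complications of more than anticipated significance or more than usual frequency. That could be read as a filter. But the SAE sentence speaks only of an event, and 9.3 brings in limb infection regardless of severity. The filter cannot be relied on.

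4. **Does the UADE clause require surprise?** The first part has two conditions: the effect is related to the device, and it meets the SAE definition. The word unanticipated appears in the defined term and in the second part, not as a condition of the first. A treated, device-related skin blister, a type of event listed in 9.3, satisfies both conditions as written.

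5. **Where do the counts go?** Table 14.3.1 attaches a p-value to the SAE row, from a Kruskal-Wallis test controlling for stratification. Section 11.4 sends SAEs to the DSMB. Table 3 in section 11.5 sends UADE reports to the sponsor, the IRB and the DSMB.

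6. **Are the reporting times consistent?** Section 9.2 gives 72 hours for a UADE report to the sponsor. Table 3 gives up to 10 working days for a report that also goes to the sponsor. A site that follows Table 3 can breach 9.2. The two passages must be reconciled.

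**The case against.** The strongest reply is that this is loose drafting with a safe direction of error. A broad definition over-reports, which is cautious for subjects. Section 9.3 does not say that its listed events are non-serious, so an infection can properly be both a pre-defined AE and an SAE. In the UADE sentence, the defined term itself and the phrase about any other unanticipated problem suggest that the first part was meant to cover unanticipated effects only. All of this is fair. What remains is that a reporting definition should not depend on inferred intent, and that over-reporting which differs by site does not give an interpretable comparison.

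Three stronger readings are tempting, and the documents do not support them.

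- **That every debrided worsening ulcer is an SAE.** Under 7.7 debridement is as-needed care of an ulcer that every subject has at entry, and the synopsis lists it among visit procedures in both arms. It need not result from an adverse event. The text leaves this open, so infection is the example to rely on.
- **That the SAE comparison is biased by contact frequency.** Control subjects have up to 16 scheduled treatment visits and ACTitouch subjects 7. But section 6.5 adds ACTitouch support contacts: 2 early ones plus 9 in weeks without a visit, which is 11, and 7 + 11 = 18. Section 6.7 also allows unscheduled visits. A remote contact cannot deliver treatment, but a symptomatic infection has a roughly weekly route to detection in both arms.
- **That grave events would be hidden.** SAP Table 14.3.3 tests ulcer infection and hospitalization for worsening VLU on separate rows. SAEs are listed one by one with severity, causality, outcome and verbatim description. Worsened or new heart failure is its own pre-defined AE. The SAE total is not a named safety endpoint in section 12.3.4.

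**Conclusion.** The point holds as a defect of definition. As written, section 9.2 turns a routinely treated study-limb infection into an SAE, and a device-related one into a UADE whether or not it was anticipated. The SAE row in Table 14.3.1 and the SAEs before the DSMB would mix events of very different gravity and could depend on site interpretation.

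The size cannot be stated, because neither document gives an event rate. A reader might try to supply one. Suppose, purely as an assumption, that 10% to 25% of subjects have a treated infection, that 2% to 5% have an event meeting another criterion, and that the two do not overlap. The ratio of SAEs with and without the intervention criterion then runs from (10 + 5)/5 = 3 to (25 + 2)/2 = 13.5. So wide a range, from invented rates, supports no figure for the inflation.

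The conclusion rests on a literal reading by at least some sites, and on the retained text of an abbreviated SAP. The primary endpoint and the non-inferiority test are unaffected.

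**What to change.** - **Section 9.2, intervention criterion.** Add a qualifier that states which interventions make an event serious, and say that routine protocol wound care and outpatient treatment of a pre-defined AE do not by themselves do so.
- **Section 9.2, UADE.** Put the word unanticipated into the first part of the definition.
- **SAP Table 14.3.1.** Show SAEs that qualify by intervention alone on a separate row from those that meet death, life threat, disability or hospitalization. This needs the criterion met to be recorded for each SAE. The documents do not show whether the case report form does so; if not, it would have to be assigned from the verbatim descriptions before the comparison is run.
- **Section 9.2 and Table 3.** Reconcile the 72-hour and 10-working-day times for UADE reports.

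The cost is a short amendment to 9.2, one alignment in section 11.5 and one added table row. The downside is that fewer events would get the 72-hour report. Limb infection, skin irritation or blistering and worsening ulceration would still be reported under 9.3 whatever their severity.
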